1. LIST OF ABBREVIATIONS

Abbreviation	Definition
AE	Adverse Event
AEM	Adverse event monitoring
AEMPS	Agencia Española de Medicamentos y Productos Sanitarios (Spanish Agency of Medicines and Medical Devices)
AR	Autonomous Regions
AUC	Area under the curve
	Heng risk criteria for anti-VEGF targeted therapies; Prognostic Factors for poor Overall Survival: KPS <80 Time from diagnosis to start of treatment <1 year Anaemia Hypercalcaemia Neutrophilia Thrombocytosis 0 Factors: favourable prognosis group 1-2 Factors: intermediate prognostic group ≥3 Factors: poor prognostic group.
Classification of the prognostic group according to Heng	
Continuous CR	Continuous CR with no changes in the last recorded imaging test

	(CT).
CR	Complete Response
CR + Local treatment	Complete pharmacological response and with local treatment
CR investigator	Complete response: disappearance of all measurable lesions according to investigator's criteria in at least 2 consecutive CT scans
CRF	Case Report Form
CT scan	Computerised axial tomography
CTCAE version 4	Common Terminology Criteria (Common Terminology Criteria for Adverse Events, version 4) of the U.S. Department of Health and Human Services
CVA	Cardiovascular Accident (Stroke)
DMP	Data management plan
DOR	Duration of Response
DOR Duration of Complete Response (CR)	Duration of complete response (CR) to sunitinib; date from the first Computerised axial tomography (CT) scan in which CR was detected to the CT scan in which there was disease progression. If CR continues, continuous CR must be indicated.
DP	Disease Progression
ECOG	Eastern Cooperative Oncology Group. Scale to measure the quality of life of oncology patients with scores running from 0 to 5
eCRF	Electronic Case Report Form
EDP	Exposure during pregnancy
FDA	Food & Drug Administration
GCP	Good Clinical Practice

HFS	Hand-Foot Syndrome
IC	Informed Consent
ICH	International Conference on Harmonisation
IEC	Independent Ethics Committee
KPS	Karnofsky Performance Scale. Scale to quantify the general well-being of patients with cancer and activities of daily living
LDH	Lactate Dehydrogenase
mRCC	Metastatic Renal Cell Carcinoma
mTOR	Mammalian Target of Rapamycin
N/L Ratio	Neutrophil/lymphocyte ratio
NIS	Non-interventional study
ORR	Objective Response Rate
OS	Overall Survival
PFS	Progression-Free Survival
PR	Partial Response

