In the sorafenib expanded-access programme in the USA and Canada (Stadler *et al.*, 2010) less than 1% of patients achieved CR to treatment with sorafenib in the investigator's opinion.

➤ Retrospective data on real-world studies:

However, in real life this figure may be higher than in a clinical trial setting because the definition of CR is laxer, follow-up of patients is greater and, therefore, the opportunity to reach CR is more feasible, as there are late responders to treatment.

In daily clinical practice, the CT scan is used to assess tumour response, while in clinical trials other additional examinations may be performed, such as a bone scan or brain scans that may reveal metastases that otherwise may not be accounted for.

In the pool analysis of 3 prospective studies published by Castellano (Castellano *et al.*, 2017), 6.1% of patients achieved complete response in the investigators' opinion.

In the **retrospective Spanish SULONG study**, in which 97 patients who had had a PFS to sunitinib greater than 22 months were selected, the percentage of patients who achieved CR reached 21% with a median CR of 33 months (Puente *et al.*, 2017).

In a retrospective series from the hospital Gustave Roussy, [name] analysed 64 patients who obtained CR to TKIs with the drug only (36 cases) or with the combination of local treatment (28 cases); surgery, radiotherapy or radiofrequency ablation (Albiges *et al.*, 2012).

The definition of CR according to RECIST 1.1 criteria was the disappearance of all known target lesions, the disappearance of all non-target lesions and the absence of new lesions.

CR had to be confirmed with two consecutive CT scans performed with at least 4 weeks between them. Confirmation from the oncologist and radiologist was required at each site.

The treatment received was sunitinib in 59 patients and sorafenib in the remaining 5. The dose and regimen used for sunitinib was 50 mg in a 4/2 regimen and sorafenib at 800 mg/24 hours.

Most of the patients had a favourable (22 cases) or intermediate (39 cases) prognosis. However, 3 patients were classified as having a poor prognosis.

Almost all the patients displayed clear cell histology (60 out of 64 patients) and all had been nephrectomised.

There were 26 patients who had a single metastatic location versus 23 who had 2 affected organs and 15 patients who had 3 or more locations.

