8.2. Scope

The patient population eligible for this study includes any patient with advanced or metastatic renal cell cancer who has been treated with Sunitinib and has achieved CR of the tumour and its metastases at any time during treatment and according to the usual assessment criteria in daily clinical practice, whether it was obtained with sunitinib alone or if a local treatment was needed to eradicate all the lesions: (surgery of the residual metastases, radiofrequency ablation or radiotherapy)

The requirements for inclusion are:

1. These patients must have received Sunitinib as first-line treatment, according to their Summary of Product Characteristics.
2. Data collection: clinical, safety, response in patients with advanced renal cancer.

The study is expected to be conducted in 50 sites throughout Spain to reach the maximum number of patients in the registry.

The collection of cases will start at each hospital after the agreement with the site is signed and all study documentation has been completed and the person appointed by the sponsor delivers training on the procedures and objectives of the protocol.

As many patients at the site who meet the inclusion criteria and none of the exclusion criteria may be included.

This is an observational study designed to reflect routine clinical practice, there will be no interference with the routine daily medical care of patients with renal cancer.

The data collected will correspond to the data normally included in the medical records; demographic variables of the patients (never personal data that could lead to patient identification), age at the time of starting treatment, routine laboratory values required in the diagnosis and control of this condition, patient performance status and clinical status. It is also intended to collect treatment compliance, tolerability and adverse events and effectiveness of treatment.

As this is a retrospective observational study, no additional material or additional examinations not contemplated in regular practice will be required.

A patient who meets the inclusion criteria, who does not meet any exclusion criteria, and who has received treatment with sunitinib prior to participation in the registry will be considered assessable.

No patient follow-up period is established and there are no patient interviews, as there is only one time when the patient's data are reviewed; this will be when the investigator completes his/her CRF.

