Time in Sunitinib treatment once the CR has been reached	Treatment data	Treatment data
Local treatment techniques of residual lesions	Treatment data	Treatment data
PA (pathological anatomy) of metastasectomy: histology and degree of necrosis	Disease data	Disease data
Adverse effects related to Sunitinib treatment of the highest degree achieved	Treatment data	Treatment data
Serious side effects (SAEs) during Sunitinib treatment	Treatment data	Treatment data
Pharmacological group of 2nd line treatment after disease	Treatment data	Treatment data

PFIZER CONFIDENTIAL

progression after a period of time in CR (TKI, mTOR, Immunotherapy)		
Cause of death	Disease data	Disease data

For this observational study, demographic variables that do not imply personal data with which the patient can be identified will be recorded, medical history including date and stage of the disease at diagnosis and progression, surgical treatment, histology, risk criteria for the disease before of its onset, comorbidities, blood and biochemical hematimetry, history of Sunitinib treatment, associated adverse events, clinical efficacy, dose, date of onset and subsequent treatments, as well as the patient's condition (alive, deceased), and date of last contact.

A full description of the variables, including the definitions, will be detailed in the Statistical Analysis Plan of the study. **Source documents**

The investigator will have full responsibility for the accuracy and authenticity of the clinical and laboratory data included in the CRFs at all times.

The source document of this study will be the patient's medical records in their clinical history, including their surgical records that will be kept at the centre where the study is conducted. All data will be captured in a CRF.

If special problems and/or questions arise or governmental requirements to carry out an inspection, it will be necessary to access, in addition, to the complete file of the study, as long as the right to anonymity of the patients is protected.

The information collected in the CRFs must match the data from the medical records.

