8.10. Other aspects

For the inclusion of patients in the study, the investigator should review the inclusion/exclusion criteria

The request for informed consent is not required in the case of not conducting an interview with the patient and to ensure the process of data dissociation in such a way that in the information that is handled from the clinical history there is no personal data, such as stated in order SAS/3470/2009 of December 16 on observational post-authorization studies.

These are patients who in some cases have already died and in others contact has been lost. Some patients may continue with routine visits for follow-up. In these cases, the investigator agrees to send the patient a privacy notice.

With the data available in the clinical history, the requested information will be recorded in the CRF in order to analyze the study variables.

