- 2) End date and reason
- 3) Date of progression
- 4) Date of and reason for death
- 5) Post-Sunitinib treatments (another TKI, mTOR, immunotherapy)

The following aspects will be assessed using the variables collected:

- **Time from nephrectomy to the start of systemic treatment:** defined as the time interval from the day of the nephrectomy to the day treatment with Sunitinib started.
- **Time to CR:** defined as the time interval from the day treatment with Sunitinib started until the day the complete response is documented in the first CT scan without lesions.
- **Duration of treatment with Sunitinib once CR is reached:** defined as the time interval from the day on which the complete response is documented until the day that the definitive discontinuation of the treatment is confirmed, either at the patient's own decision or at the doctor's decision.
- **Time to progression (TTP):** defined as the time interval from the day on which the complete response is documented until the first day that objective tumour progression, if any, is observed.
- **Time to change of treatment:** in patients who continue treatment with Sunitinib once the lesions have disappeared, it is defined as the time interval from the day on which the complete response is documented until the first day on which the change of treatment due to unacceptable toxicity is documented, as applicable.
- **Time to death:** defined as the time interval from the day on which the

Pfizer Confidential

complete response is documented to the day on which death from any cause is documented, if it occurs.

- **Duration of complete response (DOR):** defined as the time interval from the date on which the complete response to Sunitinib is identified until the date of the CT scan conforming tumour progression, the change of treatment due to unacceptable toxicity, death from any cause or until the date of the last follow-up at the close of the study. It represents the time that the patient survives without signs of disease.

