- Time on treatment with Sunitinib until complete remission of lesions, calculated as the difference between treatment start date and CR confirmation date (2nd CT scan).
- Duration of complete remission (DOR)
- Progression-free survival (PFS) or time from remission to disease progression, change of treatment due to unacceptable toxicity or death. It will be calculated as the time elapsed from the RC confirmation date (2nd CT scan) until the date of progression/death or change of treatment for unacceptable toxicity, as applicable, or else it will be censored on the date of the last patient follow-up.

Taking into account the asymmetry normally observed in the distribution of survival times and that follow-up periods may be uneven (different study entry date), the Kaplan-Meier method will be used to estimate the median time to CR together with its 95% confidence interval. The median will indicate when complete remission of the disease occurred in 50% of patients.

In order to find associations between time to CR and the baseline features of both patient and tumour, a log-rank test will be used for comparison between groups and the determination of the statistical significance of the correlation between each of the baseline variables and the time to complete remission of disease. The following baseline characteristics are considered:

[figure not shown]
- Demographic characteristics
- Comorbidities
- Tumour data
- Prior nephrectomy in the treatment of metastatic renal cancer
- Classification of the risk group according to Motzer and/or Heng criteria.
- Patient's baseline status, including ECOG grade, presence of anaemia, corrected calcium, LDH levels, neutrophil and platelet levels.

This analysis will establish which baseline characteristics are associated with a shorter complete response time to treatment.

As part of the secondary objectives, the doses and treatment regimens observed in the sample will also be descriptively summarised by means of absolute and relative frequencies. In the case of changes in the treatment dose, the frequency of patients with dose increase, dose reduction and changes in the rest regimen will be specified. Similarly, the most frequent reasons for changes in dosage and/or treatment regimen to RC will be reported.

Frequencies of the type of treatment received will be presented, depending on whether it

Pfizer Confidential

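### Event-free patients are followed for CR duration and PFS to an undefined last follow-up rather than to the last lesion-free CT, so the Kaplan-Meier medians can be too long by an amount the documents do not fix

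*SAP*

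**What the plan says.** SAP 7.2.4 measures PFS from confirmed CR to progression, death or change of treatment for unacceptable toxicity, "or else it will be censored on the date of the last patient follow-up". SAP 5 ends DOR at the CT confirming progression, at toxicity-driven treatment change, at death, or "until the date of the last follow-up at the close of the study". Neither section defines last follow-up or links it to a scan. The SAP 5 definition of time to progression has no censoring rule at all.

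The protocol ties remission to imaging. Its abbreviations list ends DOR at the CT showing progression and describes an ongoing remission as "Continuous CR with no changes in the last recorded imaging test". The rationale (section 6) adds: "In daily clinical practice, the CT scan is used to assess tumour response".

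The only last-status information named among the protocol variables is vital status and a contact date: "as well as the patient's condition (alive, deceased), and date of last contact". A date of last lesion-free imaging is not listed in the protocol variables or in SAP 5. The study sets no imaging timetable, and records are reviewed once (Protocol 8.2: "No patient follow-up period is established and there are no patient interviews"). No section limits the interval between last scan and last follow-up or plans a sensitivity analysis on it.

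**The concern.** The end of remission is dated mainly by CT, while its continuation is dated by follow-up of any kind. When follow-up runs past the last CT, Kaplan-Meier keeps the patient at risk and event-free through a period in which a relapse visible only on CT could not be recorded. The numerator loses events and the denominator keeps the time, so the curve sits too high.

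Median duration of CR is a named secondary objective (Protocol 7.2, SAP 2.2). PFS also enters the Cox model that SAP 7.2.4 says will support recommendations on treatment strategy after CR. CRs may date from 2007 and data collection runs to July 2019, so long intervals between last scan and last contact are possible. The documents do not say how common they are.

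**Working it through.** The plan gives no expected DOR or PFS for this registry, so there is no figure to reproduce. What can be checked is the direction of the effect and its size under stated assumptions.

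**Inputs from the documents.** About 90 patients (Protocol 8.5). Kaplan-Meier medians (SAP 7.2.4). Two illustrative true medians from Protocol 6: 27.6 months (PFS from CR, Czech registry) and 7.9 months (CR to relapse, single-centre series, TKI alone).

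**Assumed inputs.** Exponential time to relapse. Time from CR to record review uniform over 9-138 months. 30% of patients last contacted before review. Last CT 12-24 or 12-36 months before last contact in 25% or 50% of patients, and within 6 months in the rest. A share p of relapses in the gap is found without a scheduled scan.

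**Step 1: direction, by hand.** For exponential data, rate = events / person-time. Let c be the share censored under last-CT censoring, g the mean extra unscanned time per censored patient, and λ = ln 2 / median. With no gap relapse detected, last-follow-up censoring multiplies the median by

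1 + c·g·λ / (1 − c).

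At 27.6 months, λ = 0.693 / 27.6 = 0.0251.

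- c = 0.3, g = 6: 1 + 0.3 × 6 × 0.0251 / 0.7 = 1.06, giving 29.4 months.
- c = 0.3, g = 12: 1.13, giving 31.2 months.
- c = 0.5, g = 6: 1.15, giving 31.8 months.
- c = 0.5, g = 12: 1.30, giving 35.9 months.

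The factor cannot fall below 1, so the estimate is unchanged or longer. The formula describes the exponential rate estimate. It overstates the effect on a short Kaplan-Meier median, so size is taken from simulation.

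**Step 2: size, by simulation.** True median 27.6 months. The middle column is the SAP rule. The right-hand column censors event-free patients at the last CT but still counts every later event.

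| Patients with a 12-24 month gap | p | Last follow-up (SAP) | Last CT, event-free patients only |
|---|---|---|---|
| 25% | 0 | 30.0 | 27.7 |
| 25% | 0.5 | 28.7 | 26.7 |
| 25% | 1 | 27.5 | 25.8 |
| 50% | 0 | 31.7 | 27.7 |
| 50% | 0.5 | 29.3 | 26.1 |
| 50% | 1 | 27.6 | 25.2 |

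With gaps of up to 36 months included:

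- The SAP rule at p = 0 gives 30.0-33.6 months. The excess is 30.0 − 27.6 = 2.4 to 33.6 − 27.6 = 6.0 months, or 9% to 22%.
- At p = 0.5 the excess is about 1-3 months. At p = 1 there is none.
- If every patient's last CT lies within 6 months of last contact, the median reads about 28.6, an excess of 1.0 month.
- At a true median of 7.9 months the excess is at most about 1.7 months.

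**Step 3: check of the remedy.** Censoring only event-free patients at the last CT, with later events still counted, gives 24.6-26.8 months when some or all gap relapses are detected, which is too short. Applying the last-imaging cut to events and non-events alike gives 27.5-27.8 months in every scenario.

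**The case against.** The strongest reply is that the gap is inferred. The SAP never equates last follow-up with last contact; that date comes from a general list in the protocol. The protocol abstract links follow-up visits to CT scans in its plan for the neutrophil-lymphocyte analysis. If sites enter the date of a CT-paired visit, most or all of the bias goes. This stands as a limit on size, and it is also a reason to define the date.

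Second, unscanned time is not unobserved time. Visits can reveal symptomatic relapse, and death and toxicity-driven treatment change are seen through contact. Inclusion also accepts remission judged clinically. This stands too: a reader might infer that nobody looked for relapse after the last CT, or that the bias is certain, and the documents support neither.

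Third, last-CT censoring can itself mislead. Step 3 confirms this for a one-sided rule, so the remedy has to be symmetric.

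Fourth, precision is poor. With 90 patients and about 62 events, 95% of estimated medians fall between about 19.6 and 38.0 months, so the shift lies within sampling error. That is true, but a confidence interval does not reveal or correct a systematic shift.

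**Conclusion.** The point holds in a limited form. The stated rule lets unimaged time count as relapse-free in the Kaplan-Meier estimates of DOR and PFS, at odds with the protocol's CT-based definition of ongoing CR, and nothing elsewhere corrects it. Relative to a true median of 27.6 months, the excess runs from nil to about 6 months. It depends on assumed gap lengths, on the share of patients affected and on how many gap relapses are found clinically. None of these is in the documents, so no single figure should be quoted as the bias.

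Two stronger readings are not supported. A reader might infer that the rule distorts a comparison of stopping with continuing sunitinib. The SAP lists no subgroups (4.4), its Cox covariates are baseline conditions, dose and regimen, and type of treatment, and nothing shows that patients who stopped were scanned less. A reader might also cite Protocol 8.10 ("These are patients who in some cases have already died and in others contact has been lost") as evidence of long gaps; where contact is lost, follow-up ends as well, so it does not show contact continuing after imaging.

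The direction applies to Kaplan-Meier only. SAP 7.2.2 also summarises DOR as a plain mean and median, where treating an ongoing remission as finished pulls the other way.

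**What to change.** In SAP 5 and 7.2.4:

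- Censor DOR, PFS and time to progression at the last imaging test showing no lesions.
- Apply the rule symmetrically. A progression or death first recorded more than a pre-set interval after the last imaging is also censored at that imaging, so that late events are not counted while event-free time is dropped. Fix the interval before the data are examined. Step 3 tested the strict form; a wider interval leaves some residual bias.
- Keep date of last contact for time to death.
- Report last-follow-up censoring, with all events counted, as a sensitivity analysis.

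Collect the date of the last lesion-free imaging test by one added CRF field or query. The radiology reports that sites must hold are those proving CR, which need not include the latest scan, so this goes slightly beyond SAP wording.

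The cost is one extra date per patient, some loss of follow-up time and events, and slightly less favourable medians. The rule also assumes that the end of imaging is unrelated to the risk of relapse; the sensitivity analysis shows how far the result depends on the choice.
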